Investigational product (including active comparator and placebo) :	IDOFORM®Travel No placebo/active comparator
Centers:	Oslo University Hospital (single center)
Study Period:	Estimated date of first patient enrolled: 01.12.2015 Anticipated recruitment period: 18 months Estimated date of last patient completed: 30.11.2017
Treatment Duration:	8 weeks
Follow-up:	One follow-up consultation 2 weeks after completed therapy
Objectives	Primary: Assess the safety of a probiotic compound (IDOFORM®Travel) in combined anti-retroviral therapy (cART)-treated immunologic non-responder (INR) patients with chronic HIV infection. Secondary: i) Explore the biological effects of probiotics in cART-treated INR patient with chronic HIV infection; and ii) investigate differences between cART-treated HIV-infected INR and non-INR patients with regards to gut microbiome and mucosal barrier function.
Endpoints:	Primary endpoints: i) Adverse effects; ii) Δ plasma viral load; and iii) Δ blood CD4 count. Secondary/Exploratory endpoints: Alterations in i) Gut microbiota composition; ii) Gene expression of gut epithelial cells; iii) Frequency and activation status of CD4+ T cell subsets in gut lamina propria, including Th17 and Th22 subsets; iv) Frequency, activation status and intracellular signaling of systemic T cells; and v) Soluble

	systemic markers of chronic inflammation and immune activation.
Study Design:	
 1) Single arm, open label, consecutive case series, single center intervention study on cART-treated INR patients with chronic HIV infection 2) Subsidiary cross-sectional case control, single center study comparing cART-treated INR patients with chronic HIV infection to non-INR patients with chronic HIV infection and to healthy controls.

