2 STUDY OBJECTIVES AND RELATED ENDPOINTS

The **primary objective** of this study is to assess the safety of probiotics in cART-treated INR patient with chronic HIV infection.

The **secondary objectives** are to i) explore the biological effects of probiotics in cART-treated INR patient with chronic HIV infection, and ii) investigate differences between cART-treated HIV-infected INR and non-INR patients with regards to gut microbial composition and mucosal barrier function.

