3 OVERALL STUDY DESIGN

[figure not shown]
The primary study is a phase I, single arm, open label, consecutive case series study examining the safety of IDOFORM®Travel in patients with a confirmed diagnosis of HIV infection and continuous cART treatment >4 years and concurrent HIV (ribonucleic acid) RNA <50 copies/mL and CD4+ count <400 cells/μL >3.5 years prior to inclusion. There will be no control arm to the intervention. The primary objective is safety assessment. The secondary objective is exploratory. End points at the termination of the intervention will be compared to the parameters at inclusion. (See chart below.)

Study Period	Estimated date of first patient enrolled:	01.12.2015
	Anticipated recruitment period:	18 months
	Estimated date of last patient completed:	30.11.2017
Treatment Duration:	8 weeks	
Follow-up:	Follow-up terminated at termination of treatment	

In a subsidiary cross sectional case control study, the patients included in the intervention will at baseline (week 0) be compared with individuals with chronic HIV infection and continuous cART >4 years and concurrent HIV RNA <50 copies/mL and CD4+ count >600 cells/μL >3.5 years prior to inclusion, and with

HIV uninfected individuals, both control groups matched to cases with regards to gender, ethnicity, age, and comorbidity

Project scheme

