10.4 Statistical Analysis

Non-parametrical statistics will be applied for all analyses, two-sided tests only. Level of statistical significance defined as $p < 0.05$. Patients with missing values will be excluded from analysis of the parameter where value is missing. This study does not have any additional separate statistical analysis plan.

Primary endpoints: (see section 2.1)

i) Adverse events:

- a. Descriptive presentation of frequencies concurrent to study treatment. No comparative statistical analysis.

ii) Δ plasma HIV RNA load:

- a. Δ defined by changes between end of study (week 8) and baseline (week 0).
- b. Assessed by routine HIV RNA quantification at Dep. of Medical Microbiology, OUH.
- c. H_0 : Eight weeks treatment with probiotics does not change HIV RNA load in INR cART-treated chronic HIV-infected patients.
- d. Analyzed by Wilcoxon signed-rank test.

iii) Δ blood CD4 count:

- a. Δ defined by changes between end of study (week 8) and baseline (week 0).
- b. Assessed by routine CD4 cell quantification at Dep. of Immunology, OUH.
- c. H_0 : Eight weeks treatment with probiotics does not change blood CD4 cell count in INR cART-treated chronic HIV-infected patients.
- d. Analyzed by Wilcoxon signed-rank test.

Secondary endpoints: (see section 2.2)

The statistical analysis strategy is described below. As the efficacy assessments of this study are of exploratory nature, the exact parameters assessed and variable to be analyzed are difficult to predict. The conductance of the statistics may diverge from the planned analyses.

- Alterations are defined by:
 - Changes in *variable* between end of study (week 8) and baseline (week 0) in INR cART-treated chronic HIV-infected patients.

or

- Differences in *variable* between INR cART-treated chronic HIV-infected patients (week 0) (cases) and cART-treated immunological responding chronic HIV-infected patients (controls) and HIV negative subjects (healthy controls).
- Null hypothesis (H_0) will be formulated as:
 - H_{0-1} : Eight weeks treatment with probiotics does not alter the *variable* in INR cART-treated chronic HIV-infected patients.

or

- H_{0-2} : INR cART-treated chronic HIV-infected patients (week 0) (cases), cART-treated immunological responding chronic HIV-infected patients (controls) and HIV negative subjects (healthy controls) have equal *variable*.
- Statistical tests will consist of:

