- Composition of microbiota tentatively analyzed by principle components analysis and Monte Carlo permutation test. Microbiota diversity tentatively analyzed by Shannon index and Simpson reciprocal index.
- For single variable analyses H₀-1s analyzed by Wilcoxon signed-rank test and H₀-2s analyzed by One-way ANOVA with Bonferroni posttests.

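### Section 10.4 requires non-parametric statistics throughout, then assigns the single-variable group comparisons to one-way ANOVA, with no use of the matching and no stated set of post-tests

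*Combined protocol and SAP*

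**What the plan says.** Section 10.4 (Statistical Analysis) begins with a general rule: "Non-parametrical statistics will be applied for all analyses, two-sided tests only". It sets significance at p below 0.05 and says that there is no separate statistical analysis plan.

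For secondary endpoints the section defines two families of null hypotheses. H0-1 is no change over eight weeks in INR patients. H0-2 is equality of INR patients at week 0, non-INR patients and HIV-negative subjects. For single variables, H0-1 gets the Wilcoxon signed-rank test, and H0-2 is to be "analyzed by One-way ANOVA with Bonferroni posttests". Microbiota composition is handled separately, tentatively by principal components analysis with a Monte Carlo permutation test.

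Other parts that bear on the choice of test:

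- Section 3 describes "both control groups matched to cases with regards to gender, ethnicity, age, and comorbidity".
- Secondary objective ii (section 2) is to "investigate differences between cART-treated HIV-infected INR and non-INR patients with regards to gut microbial composition and mucosal barrier function". Hypotheses i and ii in section 1.3 likewise set INR patients against immunological responders.
- The synopsis describes the sub-study as "comparing cART-treated INR patients with chronic HIV infection to non-INR patients with chronic HIV infection and to healthy controls".
- Section 4.2 plans 20 subjects in each of the three groups.
- Section 10.4 calls the secondary analyses exploratory and allows them to diverge from the plan. Section 10.3 asks that deviations be described and justified.

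**The concern.** One-way ANOVA is a parametric method, so the assignment for H0-2 breaks the rule stated earlier in the same section. The signed-rank test for H0-1 obeys it. No transformation or distributional check is named that would reconcile the two. The analyst must set one sentence aside and could do so after seeing both results.

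Two further gaps concern the same test. It has no block, stratum or covariate, so the matching plays no part in the analysis. It also comes with a Bonferroni step whose family is not listed, so the alpha that reaches INR versus non-INR, the contrast named in objective ii, is undefined. What is at stake is reproducibility and power in the cross-sectional sub-study, for which 40 control subjects are recruited.

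**Working it through.** **Nothing to reproduce.** Section 10.1 says that sample size calculations for the secondary objectives are not feasible, and it gives no effect size or SD. Everything below the first step rests on assumed effects, skewness and correlations.

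**1. The conflict.** The general rule covers all analyses without exception. The H0-2 instruction names a parametric test. The permission to diverge does not say which of the two is the plan. No arithmetic is needed.

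**2. Choice of test at equal alpha.** Assumptions: 20 per group (section 4.2), INR shifted by 0.9 SD (on the log scale for log-normal data), HIV-negative group distributed as non-INR, two-sided alpha 0.05, untransformed data. The ANOVA contrast uses the pooled error with 3 × 20 − 3 = 57 df. Simulated power for INR versus non-INR:

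| Data | ANOVA contrast | Mann-Whitney | Difference |
|---|---|---|---|
| Normal | 80% | 77% | −3 |
| Log-normal, log-SD 0.5 | 79% | 77% | −2 |
| Log-normal, log-SD 1 | 70% | 77% | +7 |
| Log-normal, log-SD 1.5 | 55% | 77% | +22 |

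The skewed rows depend on where the third group lies, because it feeds the pooled error. At log-SD 1 and alpha 0.05/3, ANOVA power is about 51% with HIV-negative equal to non-INR. It is about 27% if HIV-negative equals INR, and about 59% if HIV-negative lies 0.9 log-SD below non-INR. The Mann-Whitney comparison of two groups does not involve the third.

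**3. The Bonferroni family, normal data, ANOVA contrast.** The noncentrality is d/√(2/n) = 0.9/√(2/20) = 2.846. Power is the probability that a noncentral t with 57 df exceeds the critical value in absolute size:

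| Post-tests | Alpha | Critical t | Power |
|---|---|---|---|
| 1 | 0.05 | 2.003 | 79.9% |
| 2 (INR vs each control group) | 0.025 | 2.302 | 70.6% |
| 3 (all pairs) | 0.0167 | 2.467 | 64.8% |

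Dividing alpha therefore costs 79.9 − 70.6 = 9.3 points with two post-tests, or 79.9 − 64.8 = 15.1 points with three.

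**4. The matching.** Section 4.3 already restricts all groups to Caucasian men, so only age and comorbidity can carry information. Suppose individually matched sets with within-set correlation ρ and a shift of 0.8 SD. The paired t-test has noncentrality [0.8/√(2(1−ρ))] × √20 with 19 df. At ρ = 0.3 this is (0.8/√1.4) × √20 = 3.02. The size and the unpaired power are simulated:

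| ρ | True size of nominal 5% ANOVA | Unpaired t power | Paired t power |
|---|---|---|---|
| 0 | 4.8% | 70% | 67.0% |
| 0.2 | 2.5% | 71% | 76.5% |
| 0.3 | 1.5% | 73% | 81.8% |
| 0.5 | 0.5% | 76% | 92.4% |

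Ignoring a useful match makes the test conservative. If ρ is near zero, pairing costs a little power.

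**The case against.** The best defence is that these analyses are secondary, exploratory and carry no power claim, that the plan openly allows them to diverge, and that deviations will be justified in the report. This stands as a limit on severity. It does not remove the conflict, because a deviation can be justified only against one defined plan.

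Several stronger readings are tempting, and the documents do not support them:

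- *ANOVA governs the whole sub-study.* It is assigned only to single-variable analyses. Microbiota composition, which is the subject of hypothesis i and part of objective ii, has its own permutation-based method.
- *Alpha is spent on contrasts outside the design.* INR versus healthy controls is announced in the synopsis and section 3. Only non-INR versus HIV-negative has no stated purpose, and the plan does not say that all three pairs will be tested.
- *A rank test is much more powerful.* Setting Mann-Whitney at 0.05 against ANOVA at 0.0167 mixes two changes. At equal alpha the rank test is slightly worse on normal data. Its large gains need strongly skewed, untransformed variables; ANOVA on log values would avoid that loss.
- *The match is worth a definite number of patients.* Section 3 does not say whether matching is individual or at group level, and no correlation is given.
- *False positives are inflated by a known amount.* The Bonferroni step does not correct across variables, but the plan gives no count of variables and labels the work exploratory.

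**Conclusion.** Section 10.4 contradicts itself on the test for single-variable H0-2 comparisons. It also leaves the use of the matching and the set of post-tests undefined. The contradiction rests on the text alone.

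The sizes are conditional on the assumptions shown above. The effect of the test choice runs from a small loss to a gain of about 22 points as skewness rises. The alpha split is a separate matter and does not depend on the kind of test. The cost of ignoring the match cannot be fixed without the matching type and a correlation, but its direction is lost power.

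This should be fixed. It is not critical, because the primary safety objective, its endpoints and its sample size are untouched.

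**What to change.** In section 10.4, replace the H0-2 instruction for single variables with wording to this effect:

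- The key contrast is INR versus non-INR, by a rank test at two-sided 0.05. INR versus HIV-negative is supportive. A three-group test (Kruskal-Wallis with Dunn comparisons) is used only if a three-group display is wanted.
- State the type of matching. If it is individual, use the signed-rank test within matched pairs. If it is at group level, use a rank test stratified or adjusted for age and comorbidity.
- Optionally, report Benjamini-Hochberg q-values within each assay family (taxa, transcripts, flow subsets, soluble markers) beside the raw p-values.

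The cost is a few sentences and a little analysis work, with no new data or patients. Section 10.3 permits changes to the plan until database lock; because the text sits in the protocol, the sponsor should check whether the amendment procedure in section 11.3 applies. There are two small statistical costs. Variables that are truly normal lose about 3 points of power. With paired analysis, a missing value in one member of a pair removes the pair for that variable under the plan's missing-data rule.

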11 STUDY MANAGEMENT

11.1 Investigator Delegation Procedure

The PI is responsible for making and updating a “delegation of tasks” listing all the involved co-workers and their role in the project. He will ensure that appropriate training relevant to the study is given to all of these staff, and that any new information of relevance to the performance of this study is forwarded to the staff involved.

11.2 Protocol Adherence

Investigators ascertain they will apply due diligence to avoid protocol deviations.
All significant protocol deviations will be recorded and reported in the Clinical Study Report (CSR).

11.3 Study Amendments

If it is necessary for the study protocol to be amended, the amendment and/or a new version of the study protocol (Amended Protocol) must be notified to and approved by the Competent Authority and the Ethics Committee according to EU and national regulations.

No changes from the final approved and signed protocol will be made without the Competent Authority's and the Ethics Committee's prior written approval of an amendment. Exceptions are when i) necessary to eliminate immediate hazards to the study subjects, or ii) when the change involves only logistics or administration. The investigator will sign the protocol amendment.

11.4 Audit and Inspections

Authorized representatives of a Competent Authority and Ethics Committee may visit the centre to perform inspections, including source data verification. Likewise the representatives from sponsor may visit the center to perform an audit. The purpose of an audit or inspection is to systematically and independently examine all study-related activities and documents to determine whether these activities were conducted, and data were recorded, analyzed, and accurately reported according to the protocol, ICH GCP, and any applicable regulatory requirements. The PI will ensure that the inspectors and auditors will be provided with access to source data/documents.

12 ETHICAL AND REGULATORY REQUIREMENTS

The study will be conducted in accordance with ethical principles that have their origin in the Declaration of Helsinki and are consistent with ICH/Good Clinical Practice and applicable regulatory requirements. Registration of patient data will be carried out in accordance with national personal data laws.

12.1 Ethics Committee Approval

The study protocol, including the patient information and informed consent form to be used, must be approved by the regional ethics committee before enrolment of any patients into the study.

The investigator is responsible for informing the ethics committee of any serious and unexpected adverse events and/or major amendments to the protocol as per national requirements.

12.2 Other Regulatory Approvals

The protocol will be submitted and approved by the applicable competent authorities before commencement of the study.

The protocol will also be registered in www.clinicaltrials.gov before inclusion of the first patient.

12.3 Informed Consent Procedure

The investigator is responsible for giving the patients full and adequate verbal and written information about the nature, purpose, anticipated benefit, potential hazard, and insurance arrangements of the study. They will be informed as to the strict confidentiality of their patient data, but that their medical records may be reviewed for trial purposes by authorized individuals other than their treating physician.

It will be emphasized that the participation is voluntary and that the patient is allowed to refuse further participation in the protocol whenever she/he wants. This will not prejudice the patient's subsequent care. Documented informed consent must be obtained for all patients included in the study before they are registered in the study. This will be done in accordance with the national and local regulatory requirements. The investigator is responsible for obtaining signed informed consent.

A copy of the patient information and consent will be given to the patients. The signed and dated patient consent forms will be filed in the Investigator Site File binder.

12.4 Subject Identification

The investigator is responsible for keeping a list of all patients (who have received study treatment or undergone any study specific procedure) including patient's date of birth and personal number, full names and last known addresses.

The patients will be identified in the CRFs by patient number, initials, and date of.

13 TRIAL SPONSORSHIP AND FINANCING

This study is initiated and conducted by the investigators. The study is funded by the K.G. Jebsen Inflammation Research, Centre which is sponsored by the University of Oslo and Oslo University Hospital in addition to the gross funding from the K.G. Jebsen Foundation.

Additional research grant applications for the study may be submitted to the regional health authorities (Helse Sør-Øst RHF).

Proposal for Investigator Initiated Trial programs at the company manufacturing the investigational product may be submitted.

14 TRIAL INSURANCE

The PI has insurance coverage for this study through membership of the Drug Liability Association (see <http://www.laf.no> for more details).

15 PUBLICATION POLICY

Upon study completion and finalization of the study report the results of this study will either be submitted for publication and/or posted in a publicly assessable database of clinical study results.

The results of this study will also be submitted to the Competent Authority and the Ethics Committee according to EU and national regulations.

All personnel who have contributed significantly with the planning and performance of the study (Vancouver convention 1988) may be included in the list of authors.

